## 11 STATISTICS

### 11.1 Analysis Populations

For purposes of analysis, the following populations are defined:

Safety population: All enrolled subjects who take at least 1 dose of study intervention.

- Full Analysis Set (FAS): FAS consists of subjects in the safety population who had at least 1 post-baseline assessment of both TETRAS-PS CCI . FAS will be used to summarize all efficacy data.

Commercially Confidential Information

- Exposed Population (EP): The exposed population includes all subjects in the Safety population who are at least 90% compliant with study treatment

Commercially Confidential Information

Selected efficacy analyses will be repeated in this population if this population differs from FAS.

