- **Time since first ET symptom** = Day 1 (Visit 3) date - Date of first ET symptom as recorded on the Disease History case report form (CRF) + 1
- **Time since ET diagnosis** = Day 1 (Visit 3) date - Date of ET diagnosis as recorded on the Disease History case report form (CRF) + 1
- **Study drug compliance** (capsule count) = total number of capsules taken / total number of expected doses from the first dose date to the last dose date, inclusive \* 100%.

- **Number of expected doses** for subjects who completed study treatment = number of capsules taken at the clinic + number of capsules dispensed for self-administration at home = [Day 14 (Visit 5) date – Day 1 (Visit 3) date + 1] x 6 capsules/day

Expected doses are summed up to the point of discontinuation (eg, if a subject discontinued, only planned doses up to that discontinuation day are counted in the denominator).

- **Number of capsules taken** = number of expected doses - number of capsules lost - number of unused capsules returned at next clinic visit, as collected in the case report form (CRF).

For subjects who discontinued and did not return remaining capsules, the number of capsules taken will include all doses up to the last dose the subject reported, or the discontinuation date (the second dose on that day will be excluded in this calculation).

For treatment completers with additional treatment (for example the subject received study treatments for 15 days) their number of expected doses remains 84. Thus, the resulting compliance rate will likely be over 100%.

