### 7.4. Exposure and Compliance

All subjects were expected to receive treatment twice daily for 14 consecutive days for a total of 28 doses. Total number of doses taken, number of missed doses, and compliance (%) will be summarized and listed for the Safety Population. Compliance via capsule count is defined in Section 6.1.8 as the rate of actual number of doses taken compared to the intended number of doses taken during the 2-week treatment period. Treatment compliance (rounded to the whole number) will also be categorized as <70%, ≥70 to 79%, ≥80 to 89%, ≥90% to 100%, and >100%.

Commercially Confidential Information

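### SAP 6.1.8 and 7.4 give compliance different denominators, and the capsule count in 6.1.8 is inconsistent, so a full-intake early stopper can score 100% and meet the visible 90% exposure criterion

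*SAP*

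**What the plan says.** SAP 7.4 states that subjects were to be treated "twice daily for 14 consecutive days for a total of 28 doses". It refers to 6.1.8 for the definition of compliance and describes that definition as "the rate of actual number of doses taken compared to the intended number of doses taken during the 2-week treatment period".

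SAP 6.1.8 gives the ratio as "total number of capsules taken / total number of expected doses from the first dose date to the last dose date, inclusive", with expected capsules counted as days "x 6 capsules/day". For a subject who discontinues, "only planned doses up to that discontinuation day are counted in the denominator". The footnote to the Table 14.1.5.1 shell repeats that cut and also mentions the 28 doses.

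For the numerator, 6.1.8 starts from the expected number and subtracts capsules lost and capsules returned unused. The shell footnote starts from the number dispensed and subtracts those not taken and those returned. For a discontinued subject who does not return capsules, 6.1.8 counts to the last reported dose or to the discontinuation date, with the note that "the second dose on that day will be excluded in this calculation".

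Protocol 11.1 says: "The exposed population includes all subjects in the Safety population who are at least 90% compliant with study treatment". Redacted text follows directly. SAP Table 5 and Listing 16.2.3 still name the Exposed Population. SAP 8 and the visible efficacy shells name the Full Analysis Set and the Per-Protocol Population.

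**The concern.** Section 7.4 describes how much of the planned course was taken. Section 6.1.8 measures adherence up to the point of stopping. These agree for a subject with a full 14-day course and differ for every early discontinuation.

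A ratio that ends at discontinuation cannot tell a few days of drug from two weeks. Used as a 90% threshold, it does not select for exposure, which is what the name of the Exposed Population suggests it should do. SAP 6.1.8 also uses a discontinued subject's early termination value as the Day 14 value, and Protocol 6.2 gives no study drug at that visit. If no redacted condition prevents it, a Day 3 stopper could contribute to an Exposed estimate at Day 14. With about 30 subjects (Protocol 11.2.4), one subject is 1/30, about 3% of the sample.

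The numerator is a separate problem. Identical intake can give values on both sides of 90%, so two programmers following the text could classify the same subject differently.

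**Working it through.** **Plan's own figure.** 14 days × 6 capsules/day = 84 capsules, and 28 doses × 3 capsules = 84. This agrees with 6.1.8, where for completers with extra treatment "their number of expected doses remains 84".

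**Setting.** A subject takes all 6d capsules and stops at the end of Day d. Four ratios follow from the text:

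- A. True intake (or the shell numerator) over the cut denominator: 6d / 6d.
- B. Non-returner counted to the discontinuation date, that day's second dose (3 capsules) dropped from the numerator, the whole day kept in the denominator: (6d − 3) / 6d.
- C. Returner, 6.1.8 numerator read literally: (6d − returned) / 6d. Quantities dispensed are not stated. The schedule shows dispensing on Days 1 and 7, so I assume 42 capsules for Days 1 to 7, giving returned = 42 − 6d.
- D. True intake over the planned course, as 7.4 describes: 6d / 84.

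| Stop at end of Day | A | B | C (42 assumed) | D |
|---|---|---|---|---|
| 2 | 100% | 75.0% | −150.0% | 14.3% |
| 3 | 100% | 83.3% | −33.3% | 21.4% |
| 4 | 100% | 87.5% | 25.0% | 28.6% |
| 5 | 100% | 90.0% | 60.0% | 35.7% |
| 7 | 100% | 92.9% | – | 50.0% |
| 12 | 100% | 95.8% | – | 85.7% |
| 13 | 100% | 96.2% | – | 92.9% |

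Day 4 written out: A = 24/24; B = 21/24; C = (24 − 18)/24 = 6/24; D = 24/84. If all 84 capsules were dispensed at once, C for Day 4 is (24 − 60)/24 = −150%. C is left blank from Day 7 because it then depends on the second dispensing.

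**The 90% line.** Against 84 capsules, 0.90 × 84 = 75.6, so 76 capsules are needed. In whole doses that is 26 (78/84 = 92.9%), or every dose through Day 13. A full-intake stopper before Day 13 is above 90% under A and below it under D.

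**End date.** The ratio in 6.1.8 runs to the last dose date, but the discontinuation rule runs to the discontinuation day. If the last dose is at the end of Day 4 and discontinuation is recorded on Day 5, 6 or 7, the first reading gives 24/24 = 100%. The second gives 24/30 = 80.0%, 24/36 = 66.7% or 24/42 = 57.1%.

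**Changing the denominator alone.** If the expected count becomes 84 and the literal numerator stays, a Day 3 stopper who returns 24 capsules (same 42 assumption) scores (84 − 24)/84 = 60/84 = 71.4%. True intake is 18/84 = 21.4%.

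**The case against.** Compliance while on treatment is a legitimate measure. Dividing by 84 mixes adherence with discontinuation. Section 7.4 defers to 6.1.8, and the shell footnote states the 28 doses and the cut side by side, so the cut looks deliberate. Changing the wording of 7.4 would remove the mismatch just as well. This stands as a defence of reporting the ratio. It does not make the ratio usable as an exposure filter, and it leaves the numerator faults in place.

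Four stronger readings are tempting, and the documents do not support them:

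- A reader might infer that every full-intake early stopper scores 100%. Only true intake or the shell numerator gives that. Rules B and C give less for Days 2 to 5.
- A reader might infer that returning the bottle alone decides the side of 90%. The dropped second dose belongs most naturally to the discontinuation-date fallback. A non-returner whose last reported dose was the second of the day can still score 100%. Within the fallback, only stops on Days 1 to 4 fall below 90% (Day 1: 3/6 = 50.0%).
- A reader might infer that early stoppers do enter the Exposed Population. The 90% sentence runs into a redaction, SAP 5 has one where a population may be defined, and SAP 8 and the shells use Per-Protocol. Membership cannot be confirmed.
- A reader might infer that poor tolerability is concealed. The primary endpoint, treatment-emergent adverse events in the Safety Population, does not use compliance. Disposition with reasons, events leading to withdrawal and number of doses taken are all reported, the last in the same table as compliance.

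**Conclusion.** The conflict between 7.4 and 6.1.8 is in the unredacted text and affects every early discontinuation. A full-intake stopper after Day 3, 7 or 12 can score 100% under 6.1.8 but has taken 21.4%, 50.0% or 85.7% of the planned course, and can meet the visible 90% criterion. Whether that leads to membership depends on redacted text, and on settling whether the Exposed or the Per-Protocol Population is used.

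Section 6.1.8 also fails on its own terms. The non-returner fallback understates full intake (75.0%, 83.3% and 87.5% for Days 2, 3 and 4), reading the discontinuation day as counted in full in the denominator. The literal numerator for a returner subtracts capsules meant for later days from a count that has already been cut. It can even go negative, by an amount that depends on the assumed quantity dispensed.

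The effect is confined to the compliance summary and any population built on it. The primary safety analysis is unaffected.

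**What to change.** In SAP 6.1.8 and the Table 14.1.5.1 shell:

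1. Define capsules taken as capsules dispensed, plus any taken in clinic from a separate supply, minus returned, minus lost or not taken. Subtract each capsule only once.
2. Choose one end date for discontinued subjects (last dose date or discontinuation day), and treat that day the same way in numerator and denominator.
3. Where the Exposed Population is still used, apply the 90% criterion to the planned 84 capsules. Otherwise remove it from Table 5 and Listing 16.2.3, so that they agree with SAP 8.
4. Report compliance while on treatment as a separately labelled measure, and say which measure feeds the compliance categories.
5. Reword 7.4 and the shell footnote to match.

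Items 1 and 3 must be made together, as the 71.4% result shows. A subject dosed fully through an in-window Day 13 visit still passes (78/84 = 92.9%).

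The cost is SAP wording and one extra derived variable from counts already collected. The planned-course measure will be somewhat lower than the current one, and the Exposed Population may be smaller. How much smaller cannot be stated without the number and timing of discontinuations.

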**Programming note:** Concatenate specify text for Treatment Type, Trigger Type, Frequency Type as shown above if the answer is "OTHER"

Listing 16.2.5.1  
Study Drug Administration  
All Subjects

Subject ID	Protocol Amendment	Study Visit	Administered Proper Dosage of Study Drug?	Reason Dose Not Administered	Date/Time of In-Clinic Administration (Study Day)	Date/Time of Last Dose Prior to Clinic Visit (Study Day)
XXXXXX	X.X	XXXXXXX	Yes	XXXXXXXXXXXXXXXXXX	DDMMYY/HH:MM	DDMMYY/HH:MM
	X.X	XXXXXXX	Yes		DDMMYY/HH:MM	DDMMYY/HH:MM
	X.X	XXXXXXX	Yes		DDMMYY/HH:MM	DDMMYY/HH:MM
	X.X	XXXXXXX	Yes		DDMMYY/HH:MM	DDMMYY/HH:MM
		XXXXXXX	No			
XXXXXX	X.X	XXXXXXX	Yes	XXXXXXXXXXXXXXXXXX	DDMMYY/HH:MM	DDMMYY/HH:MM
	X.X	XXXXXXX	Yes		DDMMYY/HH:MM	DDMMYY/HH:MM
	X.X	XXXXXXX	Yes		DDMMYY/HH:MM	DDMMYY/HH:MM

Note: Study day is calculated relative to the date of first dose of study drug.  
Time for last dose prior to clinic visit is approximate.

Listing 16.2.5.2  
Drug Accountability  
All Subjects

Subject ID	Protocol Amendment	Total Daily Dose	Bottle	Date Dispensed (Study Day)	Number of Capsules Dispensed	Was Bottle Returned to the Clinic?	Date Returned (Study Day)	Number of Unused Capsules Returned
XXXXXX	X.X	300 mg BID	Bottle A	DDMMYYYY (X)	XX	Yes	DDMMYYYY (X)	XX
XXXXXX	X.X	300 mg BID	Bottle A	DDMMYYYY (X)	XX	Yes	DDMMYYYY (X)	XX

Note: Study day is calculated relative to the date of first dose of study drug.

**Programming note:** Concatenate specify text with a colon if the Capsules Dispensed is OTHER.

Listing 16.2.5.3  
Missed Doses  
All Subjects

Subject ID	Protocol Amendment	Were any Doses Missed?	Date of Missed Dose (Study Day)	AM/PM Dose	Number of Pills not Taken	Reason for Missed Dose
XXXXXX	X.X	No				
XXXXXX	X.X	Yes	DDMMYYYY (X)	AM	XX	XXXXXXXXXXXX
XXXXXX	X.X	Yes	DDMMYYYY (X)	PM	XX	XXXXXXXXXXXX

Note: Study day is calculated relative to the date of first dose of study drug (= Date of Missed Dose – first dose date + 1).

Commercially Confidential Information

Commercially Confidential Information

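### For discontinued subjects who return no capsules, SAP 6.1.8 counts recorded missed doses as taken, which contradicts the Table 14.1.5.1 footnote and can put these subjects in the wrong compliance category

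*SAP*

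**What the plan says.** SAP 6.1.8 defines compliance as capsules taken divided by the expected amount from first to last dose date. For discontinued subjects it adds that "only planned doses up to that discontinuation day are counted in the denominator".

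Capsules taken are normally the expected number less capsules lost and unused capsules returned. For discontinued subjects who did not bring capsules back there is a substitute rule: "the number of capsules taken will include all doses up to the last dose the subject reported, or the discontinuation date", with the qualification that "the second dose on that day will be excluded in this calculation".

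Two other places bear on this.

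- The footnote to Table 14.1.5.1 computes doses taken by subtracting both pills not taken and unused capsules returned. It cites Listing 16.2.5.3 as a source and makes no exception for non-returners.
- Listing 16.2.5.3 (Missed Doses) shows, for each missed dose, the date, AM or PM, the reason and the "Number of Pills not Taken". Protocol 5.5.3 also gives every subject a diary for the date and time of home doses.

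SAP 7.4 groups compliance, rounded to a whole number, as below 70%, 70 to 79%, 80 to 89%, 90 to 100% and above 100%. Protocol 11.1 sets a 90% criterion: "The exposed population includes all subjects in the Safety population who are at least 90% compliant with study treatment".

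**The concern.** When bottles come back, a missed dose shows up as unused capsules, so the general formula catches it. When they do not, the capsule count says nothing, and 6.1.8 fills the gap by treating every dose up to the cut-off as swallowed. The record that would correct this is collected, but 6.1.8 does not use it.

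The table footnote does use it. Two programmers, one working from 6.1.8 and one from the shell, could report different compliance for the same subject. Early stoppers are also the subjects whose real exposure a reader most needs in order to judge tolerability, which is part of the primary objective.

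**Working it through.** **Inputs.** Six capsules a day, from "Day 14 (Visit 5) date – Day 1 (Visit 3) date + 1] x 6 capsules/day" (SAP 6.1.8). Two doses a day of three capsules (Protocol 5.5.3). Category limits from SAP 7.4. Sample size about 30 (Protocol 11.2.4).

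**The plan's own figure.** SAP 6.1.8 says of completers with extra treatment that "their number of expected doses remains 84"; SAP 7.4 says "All subjects were expected to receive treatment twice daily for 14 consecutive days for a total of 28 doses". 14 × 6 = 84 capsules and 14 × 2 = 28 doses, so the daily figure reproduces both.

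**Discontinuation-date branch, read literally.** For a stop on Day d the numerator is all planned capsules less the second dose that day, 6d - 3. The denominator is all planned capsules through that day, 6d. Compliance = (6d - 3)/(6d) = 1 - 1/(2d).

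| Stop day | Capsules credited / expected | Compliance |
|---|---|---|
| 1 | 3/6 | 50.0% |
| 2 | 9/12 | 75.0% |
| 3 | 15/18 | 83.3% |
| 4 | 21/24 | 87.5% |
| 5 | 27/30 | 90.0% |
| 7 | 39/42 | 92.9% |
| 10 | 57/60 | 95.0% |
| 13 | 75/78 | 96.2% |

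Intake does not enter the formula. The 90% line is crossed at Day 5, and rounding to whole numbers does not move it.

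**Effect of missed doses (hypothetical subjects).** Stop on Day 10, credited 57/60 = 95.0%:

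- 6 doses missed, only the first dose due on the stop day: (19 - 6)/19 = 68.4%.
- 6 missed, the second stop-day dose untaken but kept in the denominator: 13/20 = 65.0%.
- 6 missed earlier, both stop-day doses taken: (20 - 6)/20 = 70.0%.
- 4 missed, same three bases in the same order: 15/19 = 78.9%, 15/20 = 75.0%, 16/20 = 80.0%.

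Every one of these leaves the 90 to 100% category. A single missed dose need not matter: with both stop-day doses taken, 19/20 = 95.0%, the same as the credited value.

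**Other readings of 6.1.8.**

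- Last-reported-dose branch, last dose the second of the day, denominator ending that day: 100%.
- Same branch, last dose the first on Day L: 1 - 1/(2L).
- Same branch, denominator running on to the discontinuation day: for example, last full day 5 and stop on Day 6 gives 30/36 = 83.3%.
- Stop-day second dose removed from numerator and denominator alike: (6d - 3)/(6d - 3) = 100% for every stop day.

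None of these has a missed-dose term, so under each the numerator counts missed doses as taken. A fully adherent early stopper is marked down only where the second stop-day dose leaves the numerator but stays in the denominator, or where the denominator runs past the last dose.

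**The case against.** A reader might infer three stronger claims. The documents do not support them.

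*That the plan ignores missed doses.* It does not. The Table 14.1.5.1 footnote subtracts them, the table reports the number of missed doses separately, and Listing 16.2.5.3 shows them by subject. The defect is a conflict between the 6.1.8 text and the footnote.

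*That compliance is wrong in both directions for all non-returners.* The formula 1 - 1/(2d) belongs literally to the discontinuation-date branch. The other branch uses the last reported dose, which tells when dosing ended, though not how many doses were taken. The downward error depends on how the stop-day exclusion is read. Leaving that dose out of the numerator has a plausible basis, since Protocol 6.2 gives no study drug on site at the Early Termination visit.

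*That the 90% Exposed population is misassigned.* The criterion is visible in the protocol only. The SAP definition is not visible, and SAP section 8 names the FAS and Per-Protocol populations for efficacy, although the planned table list and Listing 16.2.3 still name Exposed. An effect there is possible but conditional.

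It is also fair to say that the affected group is narrow (discontinued and no capsules returned), that compliance is descriptive, and that adverse event counts use the Safety population, which needs only one dose. Nothing shows that subjects who keep their bottles hand in complete diaries. All of this limits the consequence. None of it removes the missing deduction or the conflict.

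**Conclusion.** The point holds in a limited form. For discontinued subjects who return no capsules, 6.1.8 credits recorded missed doses as taken under every reading, and it contradicts the footnote of the table it feeds. The SAP also leaves open which branch has priority and whether the stop-day second dose belongs in the denominator.

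The error can be large for one subject (95.0% against 68.4% in the example) and can change the SAP 7.4 category. That part needs no redacted text. How many subjects are affected is not given; each is 1/30 = 3.3% of the sample. The table of stop-day values assumes the literal reading of the discontinuation-date branch, and the examples assume that missed doses were recorded. The primary endpoint is not affected. This should be corrected, but it does not threaten the trial's main conclusions.

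**What to change.** State one rule, in the same words, in SAP 6.1.8 and in the Table 14.1.5.1 footnote. For discontinued subjects who return no capsules:

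- Capsules taken = planned capsules through the last dose taken, less pills not taken according to the missed-dose record or the diary.
- Numerator and denominator end at the same AM or PM dose.
- The last reported dose takes priority over the discontinuation date.
- With neither a diary nor a missed-dose record, compliance is set to missing and flagged.

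Limit the missed-pill deduction to this group unless overlap is handled, because a capsule recorded as missed and also returned would otherwise be subtracted twice.

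Under this rule a fully adherent subject who stops after the first dose on any of Days 1 to 4 is reported at 100%, not 50.0% to 87.5%.

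The cost is a short SAP edit and a few lines of programming on data already collected. A few subjects may show lower or missing compliance.

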### **5.2 Rationale for Dosing**

The dose level of CAD-1883 is 300 mg (3 capsules of 100 mg each) twice daily, with the first dose for Day 1 taken in clinic, and the second daily dose taken 4 to 5 hours later on clinic visit Days 1, 7 and 14 only. The second daily dose for all other (at home) days will be taken 8 hours later ( $\pm 2$  hours).

Commercially Confidential Information

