Note: Percentages are n/Number of subjects in the Safety Population\*100.

Medical histories were coded using MedDRA version 21.1.

Subjects were counted once for each SOC and once for each PT.

Medical history terms are displayed by alphabetical order of SOC, then by decreasing frequency of PT within SOC, and then alphabetically by PT.

SOURCE: Listing 16.2.4.2

**Programming note:** ATC & PT text should be in title case in table, as shown in the shell. Ensure proper MedDRA version is printed in footnote.

Commercially Confidential Information

Commercially Confidential Information

Table 14.1.5.1  
Summary of Treatment Exposure and Compliance via Capsule Count  
Safety Population

Variable Statistic	Cohort-1 (N=XX)	Cohort-2 (N=XX)	Overall (N=XX)
Number of Doses Taken			
n	XX	XX	XX
Mean (SD)	XX.X (XX.X)	XX.X (XX.X)	XX.X (XX.X)
Median	XX.X	XX.X	XX.X
Min, Max	XX, XX	XX, XX	XX, XX
Number of Missed Doses			
n	XX	XX	XX
Mean (SD)	XX.X (XX.X)	XX.X (XX.X)	XX.X (XX.X)
Median	XX.X	XX.X	XX.X
Min, Max	XX, XX	XX, XX	XX, XX
Compliance (%)			
n	XX	XX	XX
Mean (SD)	XX.X (XX.X)	XX.X (XX.X)	XX.X (XX.X)
Median	XX.X	XX.X	XX.X
Min, Max	XX, XX	XX, XX	XX, XX
Compliance Category			
< 70%	XX (XX.X%)	XX (XX.X%)	XX (XX.X%)
≥ 70% to 79%	XX (XX.X%)	XX (XX.X%)	XX (XX.X%)
≥ 80% to 89%	XX (XX.X%)	XX (XX.X%)	XX (XX.X%)
≥ 90% to 100%	XX (XX.X%)	XX (XX.X%)	XX (XX.X%)
> 100%	XX (XX.X%)	XX (XX.X%)	XX (XX.X%)

Note: Percentages are n/Number of subjects in the Safety Population\*100. Subjects were to receive treatment twice daily for 14 consecutive days for a total of 28 doses. Compliance is number of doses taken / number of expected doses \* 100%. Number of doses taken is calculated as the number of expected doses (number of capsules dispensed) minus total number of pills not taken minus number of unused capsules returned, as collected in the case report form. Expected doses are summed up to the point of discontinuation (eg, if a subject discontinues early, only planned doses up to that discontinuation day are counted in the denominator).

SOURCE: Listings 16.2.5.1, 16.2.5.2, and 16.2.5.3

Table 14.1.5.2

Commercially Confidential Information

Table 14.2.1.1.1  
Summary of Central Rater TETRAS-PS Scores by Study Visit  
FAS and Per-Protocol Population

Parameter: TETRAS-PS Total Score

Study Visit Statistic	Full Analysis Set			Per-Protocol Population		
	Cohort-1 (N=XX)	Cohort-2 (N=XX)	Overall (N=XX)	Cohort-1 (N=XX)	Cohort-2 (N=XX)	Overall (N=XX)

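### SAP 6.1.8 and the Table 14.1.5.1 note count capsules under the name of doses, so a full course would print as 84 doses taken in a table whose note says 28

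*SAP*

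**What the plan says.** Protocol 5.2 fixes the content of a dose: "The dose level of CAD-1883 is 300 mg (3 capsules of 100 mg each) twice daily".

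SAP 7.4 states the planned course in doses: "All subjects were expected to receive treatment twice daily for 14 consecutive days for a total of 28 doses". The note under the Table 14.1.5.1 shell repeats it: "Subjects were to receive treatment twice daily for 14 consecutive days for a total of 28 doses". SAP 7.4 also commits to summarising doses taken, missed doses and compliance for the Safety Population, and refers to 6.1.8 for the compliance definition.

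SAP 6.1.8 works in capsules but keeps the word doses:

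- The expected number of doses for completers is the number of treatment days multiplied by six, ending in "Day 1 (Visit 3) date + 1] x 6 capsules/day".
- For completers with additional treatment, "their number of expected doses remains 84".
- Capsules taken is "number of expected doses - number of capsules lost - number of unused capsules returned at next clinic visit".
- Compliance is "total number of capsules taken / total number of expected doses from the first dose date to the last dose date, inclusive", expressed as a percentage.

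The Table 14.1.5.1 shell has a row labelled *Number of Doses Taken*. Its note says "Number of doses taken is calculated as the number of expected doses (number of capsules dispensed"), from which it subtracts pills not taken and unused capsules returned. No visible text divides capsules by 3.

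**The concern.** The SAP gives one named quantity, the expected number of doses for the full course, as 28 in two places and as 84 in a third. This goes beyond loose wording in a definition, because the table note carries the capsule count into a printed row labelled as doses. A programmer who follows the note produces a figure that contradicts the first lines of that note.

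The row *Number of Missed Doses* has no derivation in the visible text. Listing 16.2.5.3, one of the table's sources, has an AM/PM dose column and a separate column for pills not taken, so either could be counted. Taken and missed could then sit on different scales in adjacent rows.

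At stake is whether the exposure table can be read correctly. A reader of the study report who takes the row label at face value would credit each subject with three times as many doses as were taken.

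**Working it through.** **Inputs**

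- Capsules per dose: 3 (Protocol 5.2)
- Doses per day: 2; days: 14 (SAP 7.4)
- Capsules per day in the SAP formula: 6 (SAP 6.1.8)
- Stated totals: 28 doses (SAP 7.4 and the Table 14.1.5.1 note); 84 (SAP 6.1.8)

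**1. Reproduce the plan's figures.** Doses: 14 × 2 = 28. Capsules: 28 × 3 = 84, equal to 14 × 6. Both stated totals reproduce exactly, but 84 only as a count of capsules.

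**2. Apply the table note to a fully compliant 14-day subject.** Capsules dispensed − pills not taken − capsules returned = 84 − 0 − 0 = 84. This goes into the row labelled doses taken. Ratio to the true dose count: 84 / 28 = 3.0. With the missing division, 84 / 3 = 28.

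**3. Vary the last visit within the ±1 day window.** Days × 6 gives:

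| Day 14 visit held on study day | SAP 6.1.8 formula | True doses |
|---|---|---|
| 13 | 78 | 26 |
| 14 | 84 | 28 |
| 15 | 90 | 30 |

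The factor is 3 throughout. For a 15-day completer the formula gives 90, but a later sentence in 6.1.8 fixes 84, so 84 is not a strict ceiling.

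**4. Check compliance.** Under 6.1.8 the numerator and denominator are both in capsules, so the factor cancels:

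- Full compliance: 84/84 = 28/28 = 100%.
- Two doses (6 capsules) missed: 78/84 = 26/28 = 92.9%.

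**5. Missed-dose row.** The same two missed doses are 2 on the dose scale and 6 on the capsule scale. The SAP does not say which is meant.

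**6. Compare the two subtraction rules.** Take a subject who misses 6 capsules and returns them, with none lost:

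- SAP 6.1.8 (minus lost, minus returned): 84 − 0 − 6 = 78; 78/84 = 92.9%.
- Table note (minus not taken, minus returned): 84 − 6 − 6 = 72; 72/84 = 85.7%.

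The note counts the same six capsules twice. Unlike the unit label, this changes the compliance percentage. Here it moves the subject from the 90–100% category to the 80–89% category.

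**The case against.** The strongest reply is that doses in 6.1.8 is shorthand for capsules. The compliance definition is marked as a capsule count, the table title says so too, and the note gives both the 28-dose course and the capsule derivation. A reader who sees 84 can work out what it means. Listings 16.2.5.2 and 16.2.5.3 keep capsules and missed doses in separate columns, so the underlying data are unambiguous. A careful programmer might also notice the conflict.

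Much of this stands. The number 84 is a correct capsule count with the wrong unit, and the source data are sound. It does not rescue the row label: every term in the note's rule is in capsules, the row says doses, and nothing visible converts one to the other. A SAP marked as final should not rely on the programmer to correct it.

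Four stronger readings are tempting, and the documents do not support them:

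- *Compliance of 300%.* This needs the 28 of SAP 7.4 as the denominator. But 7.4 sends the reader to 6.1.8, where the expected count is defined in capsules.
- *A threefold error in total milligrams.* The visible text and shell contain no cumulative-dose variable.
- *Taken and missed doses cannot add up to the course total.* The missed-dose row has no stated derivation, so no particular sum follows from the plan. The capsule reading could be consistent, and any worked sum must also allow for the double subtraction.
- *Distortion of the primary safety results.* The visible percentages for treatment-emergent adverse events use numbers of subjects as denominators, not doses. Nor can this table be called the only exposure summary, since Table 14.1.5.2 and text after SAP 7.4 are redacted.

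**Conclusion.** The point holds as a unit error that reaches a reported row. Following the SAP exactly, *Number of Doses Taken* is too high by a factor of 3.0 (84 against 28 for a full course), and *Number of Missed Doses* could be on either scale. The effect is limited to those dose-count rows. Compliance percentages and categories do not change because of the unit, and no visible adverse-event or efficacy analysis uses the dose count. It should be corrected before the table is produced, but it does not threaten the trial's conclusions.

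This assumes that the table note is programmed literally, that a fully compliant subject is dispensed the planned 84 capsules, and that no conversion lies in redacted text.

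The double subtraction is a separate defect in the same lines, and it can change compliance. The 85.7% against 92.9% comparison assumes that missed capsules are both recorded as not taken and returned. It deserves care because Protocol 11.1 uses at least 90% compliance in defining the Exposed Population, although part of that definition is redacted.

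**What to change.** - In SAP 6.1.8, rename the quantities *expected capsules* and *capsules taken*, and state compliance as capsules taken over expected capsules.
- In Table 14.1.5.1, either report doses taken and doses missed on the 28-dose scale (capsules / 3) or relabel both rows as capsules. State the unit of the missed-dose row and which column of Listing 16.2.5.3 it uses.
- Use one subtraction rule in 6.1.8 and in the table note, written so that a capsule that is both missed and returned is subtracted once.

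The cost is wording in one SAP section and one table shell, one division if the dose scale is chosen, and one agreed subtraction rule in the program. No new data are needed.
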